If bone marrow myeloblasts between 5% and 25% and a decrease from baseline of at least 50% in the marrow myeloblasts, no detectable (or trace of residual) blasts, and no evidence of extramedullary leukemia, the response is classified as PR.

Not Evaluable (NE)/No Response (NR):

In the situation where no bone marrow assessments are performed or myeloblast value is missing, blast value from peripheral blood is missing or $\leq 2\%$, and extramedullary leukemia is missing or not done, the response will be classified as NE. In any case response cannot be categorized as CR, CRp, CRi, PR or NE, it will be categorized as NR.

Relapse:

Relapse after CR, CRh, CRp or CRi is defined as a reappearance of leukemic blasts in the peripheral blood ($>2\%$) or $\geq 5\%$ myeloblasts in the bone marrow not attributable to any other cause or reappearance or new appearance of extramedullary leukemia.

Relapse after PR is similarly defined with reappearance of significant numbers of peripheral blasts and an increase in the percentage of myeloblasts in the bone marrow to $> 25\%$ or $>2\%$ blast in peripheral blood not attributable to any other cause or reappearance or new appearance of extramedullary leukemia.

Best Response:

Best response is defined as the best measured response to treatment for all visits (in the order of CR, CRp, CRi, PR, NR and NE) post-baseline. Subjects who achieve the best responses of CR, CRp, CRi, or PR will be classified as responders. Subjects who do not achieve at least PR will be classified as non-responders.

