- CR/CRh rate after each treatment therapy

CR/CRh: CR or CRh.

Defined similarly as CR rate after each treatment therapy.

- Duration of CR, CR/CRh, CRh, CRc, response

Duration of CR is defined as the time from the date of achieving first CR until the date of first documented relapse for subjects who achieve CR. Subjects who die without report of

relapse are considered non-events and censored at their last relapse-free disease assessment date. Subjects who come off the study for HSCT will be considered non-events and censored at the time of HSCT. Other subjects who do not relapse on study are considered non-events and censored at the last relapse-free assessment date. Duration of CRh, Duration of CR/CRh, Duration of CRc and Duration of response are defined similarly as Duration of CR.

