6.1.4 Exploratory Efficacy Endpoints

[Phase 1 part]

- CR rate
Defined as the number of subjects with CR divided by the number of subjects in the analysis population. Subjects with unknown or missing response, or who provide no information on response at the end of study will be treated as non-responders and will be included in the denominator when calculating rates.
- CRp rate
Defined similarly as CR rate.
- CRi rate
Defined similarly as CR rate.
- CRc rate
Defined similarly as CR rate.
- PR rate
Defined similarly as CR rate.
- Overall response rate: CRc + PR
Defined similarly as CR rate.
- Duration of response – Duration of response is defined as the period from the first date of achieving CR, CRp, CRi, or PR to the first date of documented relapse for subjects who achieve CR, CRp, CRi, or PR. Subjects who die without report of relapse are considered non-events and censored at their last relapse-free disease assessment date. Other subjects who do not relapse on study are considered non-events and censored at the last relapse-free disease assessment date.
- Duration of CR is defined similarly as duration of response for subjects who achieved CR.
- Duration of CRc is defined similarly as duration of response for subjects who achieved CRc.

[Phase 2 part]

- Transplantation rate
Transplantation rate is defined as the percentage of subjects undergoing HSCT during the study period.
- Cumulative incidence of relapse (CIR) after 1st CR (CR1)
Defined as the time from the date of achieving CR1 until relapse. When calculating this variable, only subjects who achieved CR1 are included. Subjects alive without relapse will be censored on the date of last relapse-free disease assessment date. Although subjects who died without relapse should be treated as the subjects who occurred competing event, those

subjects will be censored at the date of death.

- Cumulative incidence of death (CID) after CR1

Defined as the time from the date of achieving CR1 until death. When calculating this variable, only subjects who achieved CR1 are included. Subjects who are alive without death will be censored at the date of last known alive.

- Time to hematopoietic recovery after each treatment cycle

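### The relapse-after-PR rule ties marrow blasts above 25% to peripheral blasts with an 'and', so read literally a marrow-only progression does not end duration of response

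*SAP*

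**What the plan says.** SAP section 6.1.1 gives two relapse rules, one after the other.

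- After any complete remission category: "Relapse after CR, CRh, CRp or CRi is defined as a reappearance of leukemic blasts in the peripheral blood" above 2%, or at least 5% "myeloblasts in the bone marrow not attributable to any other cause or reappearance or new appearance of extramedullary leukemia". Each element is enough by itself.
- After PR, introduced as being defined in a similar way: "reappearance of significant numbers of peripheral blasts and an increase in the percentage of myeloblasts in the bone marrow to" above 25%, or more than 2% "blast in peripheral blood not attributable to any other cause or reappearance or new appearance of extramedullary leukemia".

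The same section places PR in a marrow range: "If bone marrow myeloblasts between 5% and 25% and a decrease from baseline of at least 50% in the marrow myeloblasts". It also counts PR as a response: "Subjects who achieve the best responses of CR, CRp, CRi, or PR will be classified as responders".

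Two endpoints use the PR relapse rule. In section 6.1.4, Phase 1 duration of response runs from first response "to the first date of documented relapse for subjects who achieve CR, CRp, CRi, or PR". In section 6.1.3, for Phase 2, "Duration of CRh, Duration of CR/CRh, Duration of CRc and Duration of response are defined similarly as Duration of CR". In both, the only event is documented relapse. Subjects without one are censored at the last relapse-free assessment, which section 6.1.3 (under RFS) equates with the last disease assessment.

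**The concern.** The two rules are presented as parallel, but their connectives differ. After a complete remission, blood, marrow and extramedullary disease are alternatives. After PR, the marrow criterion is joined to a peripheral-blast criterion by 'and', while more than 2% peripheral blasts also stands as a separate alternative. The phrase about significant numbers of peripheral blasts is given no cut-off.

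A programmer who follows the words would not record a relapse when a PR subject progresses in the marrow only. That subject stays relapse-free for duration of response until another criterion is met or follow-up ends. Two programmers could also bracket the sentence differently and obtain different event dates from the same data.

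**Working it through.** The plan states no figure on this point, so the check is one of logic.

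**Inputs (section 6.1.1, relapse after PR).** Let A = significant numbers of peripheral blasts (no threshold given), B = marrow myeloblasts above 25%, C = peripheral blasts above 2%, D = extramedullary leukemia.

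**Step 1: marrow-only progression.** Take marrow 60%, no circulating blasts, no extramedullary disease, so A = 0, B = 1, C = 0, D = 0.

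| Reading | Relapse? |
|---|---|
| (A and B) or C or D | no |
| (A and (B or C)) or D | no |
| A and (B or C or D) | no |
| A or B or C or D | yes |

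Every bracketing that keeps the 'and' misses this case. After CR, CRh, CRp or CRi the same findings are a relapse, because marrow of 5% or more is enough.

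**Step 2: how the same visit is classified.** With marrow at 60% the visit is not CR, CRp, CRi or PR. It is not NE either, because a marrow value is present. Section 6.1.1 therefore makes it NR. Read literally, the subject is in no response at that visit and still relapse-free for duration of response.

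**Step 3: does the 25% threshold do anything?** If A means the 2% cut-off, then A = C and:

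- (C and B) or C or D reduces to C or D.
- (C and (B or C)) or D reduces to C or D.
- C and (B or C or D) reduces to C.

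B drops out each time. If A can be met at or below 2%, B matters in exactly one situation under all three bracketings: A = 1, C = 0, D = 0. Marrow-only progression is still missed.

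**Step 4: which endpoints use the PR rule.** EFS counts relapse after CR. RFS and duration of CRc start at CRc. Durations of CR, CRh and CR/CRh start at those states. OS and the primary CR rate do not use relapse. Only duration of response includes PR subjects.

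**Step 5: size, by assumption only.** The SAP gives neither a PR rate nor the share of marrow-only progressions.

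- Assume that 5% to 10% of the 80 Phase 2 subjects have PR as best response: 80 × 0.05 = 4 to 80 × 0.10 = 8. Assume that 25% to 50% of these progress in the marrow only: 4 × 0.25 = 1 to 8 × 0.50 = 4 subjects affected.
- Among PR subjects alone, assume a constant relapse hazard λ, independent censoring, and a share q of relapses that is never counted. The observed hazard is (1 − q)λ, so the median is multiplied by [ln 2 / ((1 − q)λ)] / [ln 2 / λ] = 1/(1 − q). This gives 1/0.90 = 1.11 for q = 10%, 1/0.75 = 1.33 for q = 25% and 1/0.50 = 2.0 for q = 50%.

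The second calculation describes PR subjects only. The curve for all responders would move much less if PR subjects are few.

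**The case against.** The strongest reply is that the sponsor meant alternatives. The sentence points back to the rule above it, and its two cut-offs (25% in marrow, 2% in blood) are themselves joined by 'or'. On that reading the 'and' merely lists two kinds of evidence, and marrow above 25% alone is a relapse. This reading is open and may well be the intended one. It does not remove the problem, because the text does not say it and a literal coding gives a different event.

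Several stronger conclusions that a reader might draw are not supported:

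- That marrow progression alone is never a relapse, so duration of response is overstated. This takes the literal reading as settled. How the rule will be programmed is not known.
- That marrow 60% with 1% peripheral blasts is clearly no relapse. Because the peripheral-blast phrase has no threshold, 1% might satisfy it. Only a case without circulating blasts is clean.
- That the 25% criterion has no effect. This holds only if the undefined phrase means more than 2%.
- That the rule contradicts the 25% upper limit of PR. It uses the same boundary, and leaving the PR category need not be the same thing as relapse.
- That every missed event becomes a censored one, with bias in one direction only. A subject may later meet the blood or extramedullary criterion and be counted late. A late event in a small risk set can even lower the tail of the Kaplan-Meier curve.

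It is also fair to say that duration of response is descriptive, with no hypothesis test attached, and that Phase 1 targets only 6 subjects.

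**Conclusion.** The point holds as a defect of wording with a limited effect. Taken literally, the PR relapse rule leaves out marrow-only progression, which departs from the parallel the SAP itself claims, and it relies on a quantity that is never defined. For each PR subject with marrow-only progression, the recorded duration of response would be equal or longer than under a rule of alternatives. Peripheral relapses above 2% and extramedullary relapses after PR are captured under the most direct bracketing, (A and B) or C or D.

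The size cannot be derived from the document. The range of 1 to 4 Phase 2 subjects rests wholly on the assumed PR rate and marrow-only share, and says no more than that a few subjects at most are likely to be involved. A reader might infer that the main efficacy results are at risk. They are not: the primary CR rate, OS, EFS, RFS and the durations of CR, CRh, CR/CRh and CRc do not depend on this rule. It is a minor correction, worth making because it costs so little.

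**What to change.** Restate relapse after PR as explicit alternatives, parallel to the rule after complete remission and using the SAP's own thresholds:

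- marrow myeloblasts above 25%, OR peripheral blasts above 2%, in either case with no other cause to explain them; OR
- extramedullary leukemia that returns or appears for the first time.

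Delete the undefined phrase about significant numbers of peripheral blasts together with its 'and'. Check that the result matches the protocol, which is not at hand here, and reconcile the two documents if it does not.

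The cost is one sentence of SAP text and a matching line in the derivation of duration of response. No additional data are needed. The downside is that reported duration of response may become slightly shorter.

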6.1.2 Primary Efficacy Endpoint

[Phase 1 part]

Not applicable.

[Phase 2 part]

- CR rate after induction therapy period

Defined as the number of subjects who achieve the best response of CR divided by the number of subjects in the analysis population during induction therapy period. Subjects with unknown or missing response, or who provide no information on response will be treated as non-responders and will be included in the denominator when calculating rates.

6.1.3 Secondary Efficacy Endpoints

[Phase 1 part]

Not applicable.

[Phase 2 part]

- Overall survival (OS)

OS is defined as the time from start date of the first treatment until the date of death due to any cause. For a subject who is not known to have died by the end of long-term follow-up, OS is censored at the date of last known alive.

As a sensitivity analysis, OS is defined similarly as the above, however, subjects who undergo HSCT will be censored at the time of HSCT.

- Event free survival (EFS)

The time from the date of start date of the first treatment until the date of documented relapse after CR, treatment failure or death from any cause, whichever occurs first. For a subject with none of these events, EFS is censored at the date of last disease assessment. Subject without post-treatment disease assessment will be censored at the start date of the treatment.

Treatment failure includes those subjects who failed to achieve CRc by the end of consolidation period, or who discontinued the treatment due to “lack of efficacy” without a previous response.

Treatment failure date refers to the end of treatment date for subjects with treatment failure.

- Relapse free survival (RFS)

The time from the date of achievement of first CRc until relapse or death from any cause, whichever comes first for subjects who achieve CRc. For a subject who is not known to have relapsed or died, RFS is censored on the date of last relapse-free disease assessment date.

Last relapse-free disease assessment date refers to the subject’s last disease assessment date.

- CR rate after each treatment therapy

Defined as the number of subjects who achieve the best response of CR divided by the number of subjects in the analysis population after each treatment therapy period.

Subjects with unknown or missing response, or who provide no information on response will be treated as non-responders and will be included in the denominator when calculating rates.

- CR rate without MRD after each treatment therapy

Defined similarly as CR rate after each treatment therapy. Responders achieve that the best response is CR and MRD status is negative. CRc rate without MRD after each treatment therapy will also be defined similarly.

- CRh rate after each treatment therapy

Defined similarly as CR rate after each treatment therapy.

- CRc (Composite CR) rate after each treatment therapy

CRc: CR + CRp + CRi

Defined similarly as CR rate after each treatment therapy.

- CR/CRh rate after each treatment therapy

CR/CRh: CR or CRh.

Defined similarly as CR rate after each treatment therapy.

- Duration of CR, CR/CRh, CRh, CRc, response

Duration of CR is defined as the time from the date of achieving first CR until the date of first documented relapse for subjects who achieve CR. Subjects who die without report of

relapse are considered non-events and censored at their last relapse-free disease assessment date. Subjects who come off the study for HSCT will be considered non-events and censored at the time of HSCT. Other subjects who do not relapse on study are considered non-events and censored at the last relapse-free assessment date. Duration of CRh, Duration of CR/CRh, Duration of CRc and Duration of response are defined similarly as Duration of CR.

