PD	Pharmacodynamic
PDAS	Pharmacodynamic Analysis Set
PK	Pharmacokinetic
PKAS	Pharmacokinetics Analysis Set
PR	Partial Remission
PRES	Posterior Reversible Encephalopathy Syndrome
PT	Preferred Term
QTc	Corrected Q-T Interval
QTcF	QT interval corrected for heart rate using Fridericia's factor
RBC	Red Blood Cell
RED	Recommended Expansion Dose
RFS	Relapse Free Survival
RR	Interval between 2 consecutive r waves on an ECG
SAF	Safety Analysis Set
SAP	Statistical Analysis Plan
SAS	Statistical Analysis Software
SBP	Systolic Blood Pressure
SMQ	Standardised MedDRA Queries
SOC	System Organ Class
t _{1/2}	Apparent terminal elimination half-life
TLF	Tables, Listings and Figures
t _{max}	Time of the Maximum concentration
TTE-FAS	Time-to-Event Full Analysis Set

Abbreviations	Description of abbreviations
ULN	Upper Limit of Normal
V_z/F	Apparent Volume of Distribution During the Terminal Elimination Phase after Oral Dosing
WHO	World Health Organization
WHODD	WHO Drug Dictionary
WHODD(B2)	WHO Drug Dictionary (B-2 Format)
WHODD(B3)	WHO Drug Dictionary (B-3 Format)
WOCBP	Women of childbearing potential

List of Key Terms

Terms	Definition of terms
Baseline	Last available assessments of subjects as they enter a study before they receive any treatment.
Endpoint	Variable that pertains to the efficacy or safety evaluations of a study. Note: Not all endpoints are themselves assessments since certain endpoints might apply to populations or emerge from analysis of results. That is, endpoints might be facts about assessments (e.g., prolongation of survival).
Investigational period	Period of time where major interests of protocol objectives are observed, and where the test product or comparative drug (sometimes without randomization) is given to a subject and continues until the last assessment after completing administration of the test product or comparative drug.
Registration failure	A subject who signed the ICF and met the pre-registration criteria but did not meet all inclusion and exclusion criteria by day 8. These subjects received chemotherapy but never received ASP2215.
Screening	A process of active consideration of potential subjects for enrollment in a study.
Variable	Any quantity that varies; any attribute, phenomenon or event that can have different qualitative or quantitative values.

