5.1 Full Analysis Set (FAS)

[Phase 1 part]

Subjects who meet all of the following criteria will be included:

- Received at least 1 dose of study drug
- Assessed for at least 1 efficacy variable after study drug administration

[Phase 2 part]

Subjects who meet all of the following criteria will be included:

- Received at least 1 dose of study drug
- Had at least one post-baseline bone marrow assessment

For the statistical analysis of some Time-to-Event efficacy variables, TTE-FAS will be used. TTE-FAS is defined similarly as the FAS, however, the criterion for bone marrow assessment is removed.

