6.2 Safety Variables

Safety will be assessed by evaluation of the following variables:

- Occurrence of DLTs (Phase 1 part only)
- Adverse events (AEs)

A treatment-emergent adverse event (TEAE) is defined as an AE observed after starting administration of the study drug. If the adverse event occurs on first administration date of the study drug and the onset check box is marked "Onset after first ASP2215 taken" or the onset check box is left blank, then the adverse event will be considered treatment emergent. If the adverse event occurs on first administration date of the study drug and the onset check box is marked "Onset before first ASP2215 taken", then the adverse event will not be considered treatment emergent. If a subject experience an event both before starting administration of the study drug and after starting administration of the study drug, the event will be considered as TEAE only if it has worsened in severity (i.e. it is reported with a new

start date). All adverse events collected that begin within 30 days after taking the last dose of the study drug will also be counted as TEAE, except for subjects that undergo HSCT without leaving the study and plan to resume ASP2215 treatment after HSCT. For these subjects, TEAE is defined as adverse events observed after starting administration of the study drug until the last dose before pre-HSCT visit plus 30 days, and adverse events that begin after resumption of ASP2215 and within 30 days after the last dose of ASP2215 will also be counted as TEAE. Any AEs with onset dates completely missing will be considered TEAEs in summaries. AEs with partially missing onset dates will be assumed TEAEs unless the available portion of the date indicates that the onset was strictly before start of study drug or 30 days after the last dose of study drug. Missing or partial AE onset date will be imputed per Section 7.11.1.

ASP2215-related TEAE is defined as any TEAE with at least possible relationship (possibly or probably related) to ASP2215 as assessed by the investigator or with missing assessment of the causal relationship

A regimen-related TEAE is defined as any TEAE with at least possible relationship (possibly or probably related) to study treatment as assessed by the investigator or with missing assessment of the causal relationship.

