7.2 Study Population

7.2.1 Disposition of Subjects

[Phase 1 part]

The following subject data will be presented:

- Number and percentage of subjects with informed consent, discontinued before allocation to the treatment, allocated to the treatment (overall only).
- Number and percentage of subjects who were included/excluded in each analysis set.
- Number and percentage of subjects excluded from each analysis set by reason.
- Number and percentage of subjects completed and discontinued the study, by primary reason for study discontinuation for subjects allocated to the treatment.
- Number and percentage of subjects completed and discontinued the post-study, by primary reason for post-study discontinuation for subjects allocated to the treatment.

[Phase 2 part]

- Number and percentage of subjects with informed consent, discontinued before pre-registration to the study, allocation to the treatment, discontinued before registration to the study and allocation to study drug.
- Number and percentage of subjects completed and discontinued the pre-registration period, by primary pre-registration status.
- Number and percentage of subjects completed and discontinued the registration period, by primary registration status.
- Number and percentage of subjects who were included/excluded in each analysis set.
- Number and percentage of subjects excluded from each analysis set by reason.
- Number and percentage of subjects completed and discontinued the study, by primary reason for study discontinuation for subjects allocated to the treatment.
- Number and percentage of subjects completed and discontinued the follow-up, by primary reason for follow-up discontinuation for subjects allocated to the treatment.
- Number and percentage of subjects completed and discontinued the long-term follow-up, by primary reason for long-term follow-up discontinuation for subjects allocated to the treatment.

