7.4 Analysis of Efficacy

[Phase 1 part]

The efficacy analysis will be performed on the FAS.

For response variables, best response after each treatment therapy period will be summarized. The number and percentage of subjects in each category will be presented together with two-sided exact 95% CIs based on binomial distribution. Swimmer's plot will be presented for response variables.

For time-to-event variables efficacy analysis will be summarized using descriptive statistics. The survival curve and the median will be estimated using the Kaplan-Meier method and will be reported along with the corresponding 95% CIs.

[Phase 2 part]

The efficacy analysis will be performed on the FAS and TTE-FAS. The interpretation of statistical results will be based on the FAS. The TTE-FAS will be used to analyze OS and EFS. Analysis of MRD and MR will be performed using MAS.

Primary efficacy variable

For primary efficacy variable, CR rate after induction therapy period, the two-sided 90% exact CI by Clopper-Pearson method will be calculated. The lower limit will be used to compare with the benchmark of CR rate of 55%. The number and percentage of subjects in each category and swimmer's plot will also be presented. As a supportive analysis, CR rate after induction therapy period reported by Day 60 and CR rate after induction therapy period not being dependent on RBC and platelet transfusion (No Transfusion of RBC and Platelet within 1 week prior to disease assessment) will also be calculated.

Other efficacy variables

For other efficacy variables, analysis method will be described as follows:

Categorical variables:

The number and percentage of subjects in each category will be presented together with two-sided exact 95% CIs based on binomial distribution. Swimmer's plot will be presented for response variables.

For response assessment variables, best response rate after each treatment therapy will be summarized. The number and percentage of subjects in each category will be presented together with two-sided exact 95% CIs based on binomial distribution. For subjects who undergo HSCT, any response assessment data after HSCT will not be used (i.e. for those subjects, only response assessment data before HSCT will be used).

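### Phase 2 OS and EFS appear to start at chemotherapy, but their analysis set admits only subjects who later took ASP2215, which builds in a short event-free interval

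*SAP*

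**What the plan says.** **Clock.** SAP 6.1.3 (Phase 2) says "OS is defined as the time from start date of the first treatment until the date of death due to any cause". EFS is "The time from the date of start date of the first treatment until the date of documented relapse after CR", or until treatment failure or death if either comes sooner.

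**Analysis set.** SAP 7.4: "The TTE-FAS will be used to analyze OS and EFS". SAP 5.1: "TTE-FAS is defined similarly as the FAS, however, the criterion for bone marrow assessment is removed". The other FAS criterion therefore still applies: "Received at least 1 dose of study drug".

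**Study drug.** SAP 6.2 treats this as ASP2215. The sentence beginning "If the adverse event occurs on first administration date of the study drug and the onset check box is marked" goes on to a check box about whether onset came before or after the first ASP2215 intake.

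**Order of events.** The List of Key Terms defines a registration failure as someone who passed pre-registration but had not met every entry criterion by Day 8, and adds: "These subjects received chemotherapy but never received ASP2215". In its Phase 2 list, SAP 7.2.1 names allocation to the treatment first and then those "discontinued before registration to the study and allocation to study drug".

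**Method.** SAP 7.4 plans Kaplan-Meier estimates with no delayed entry and no landmark. The only OS sensitivity analysis in 6.1.3 censors at HSCT.

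**The concern.** A survival clock should start when a subject becomes eligible to be counted. Here the clock appears to start with chemotherapy, while membership of the set depends on reaching a later event, the first ASP2215 dose. A subject who dies in between is not in the TTE-FAS. A subject who survives is in it and is credited with that interval as survival time. This is immortal time created by the definition of the set.

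The trial has one arm, so OS and EFS can be interpreted only against outside figures. The planned curve fits neither natural comparison exactly. As survival from the start of induction, it omits the earliest deaths and the registration failures. As survival from the start of ASP2215, its clock starts too early. Either way the estimate is too favourable.

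**Working it through.** **The plan's own figure.** The SAP states no figure for OS or EFS. Its only sample-size figure is power above 80% for the CR rate (70 subjects, 55% against 70%, one-sided 0.05; SAP 4.1.2). This reproduces: the exact rule is at least 46 CRs of 70, with alpha 0.045 and power 82.0%. It does not depend on the OS/EFS time origin.

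**Does *first treatment* mean chemotherapy?** The SAP does not say, so this is an inference. It rests on three points:
- Registration failures had chemotherapy and no ASP2215, so chemotherapy comes first.
- SAP 7.2.1 lists treatment and study drug as separate allocations, in that order.
- SAP 6.2 separates events related to ASP2215 from events related to the study treatment (the regimen).

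**Length of the gap.** From Day 1 to Day 8 is 7 days, or 7 / 30.4 = 0.23 months. Day 8 is a deadline for meeting the criteria, not a stated ASP2215 start day, so 7 days is an assumption.

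**Reading A: the curve is taken as survival from chemotherapy start.** Let q be the share of chemotherapy starters who die before ASP2215, and S(t) the survival of all starters. Then

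S_TTE-FAS(t) = S(t) / (1 − q), so S(t) = reported × (1 − q).

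The SAP gives no q. With assumed values and a reported 70%:
- q = 1%: 70% × 0.99 = 69.3%
- q = 2%: 70% × 0.98 = 68.6%
- q = 5%: 70% × 0.95 = 66.5%

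Alternatively, assume a constant hazard with median m, so that λ = ln 2 / m and q = 1 − exp(−λd), with d = 7 days:

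| Assumed median OS | q | 12-month OS, all starters | 12-month OS, TTE-FAS | Difference (points) |
|---|---|---|---|---|
| 12 months | 1.32% | 50.00% | 50.67% | 0.7 |
| 24 months | 0.66% | 70.71% | 71.18% | 0.5 |
| 36 months | 0.44% | 79.37% | 79.72% | 0.4 |
| 48 months | 0.33% | 84.09% | 84.37% | 0.3 |

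With d = 3 days the range falls to about 0.3 (50.29 − 50.00) down to 0.1 (84.21 − 84.09) points.

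These figures count deaths only. Leaving out registration failures who are alive adds selection that the SAP gives no means of sizing.

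**Reading B: the curve is taken as survival from ASP2215 start.** Each time is too long by the subject's own gap: 0.23 months if the gap is 7 days.

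A and B are two interpretations of one curve. Their sizes must not be added.

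**The case against.** The case on the other side has five parts.

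- **The origin is inferred.** If the sponsor means the first ASP2215 dose, the gap disappears. SAP usage is also not uniform: 7.3.1 uses *treatment* under the ASP2215 exposure heading. This stands as a limit on certainty. It does not clear the text, because the origin of two secondary endpoints would then be undefined.
- **The effect is small.** With 80 subjects and 70% survival, the standard error is √(0.7 × 0.3 / 80) = 5.1 points, so a 95% interval is about ±10 points. A bias below one point is minor beside that. This stands on size. The bias is systematic, though, and more subjects would not remove it.
- **No planned inference depends on it.** OS and EFS are descriptive, and the only stated benchmark is the CR rate of 55%. This also stands.
- **Regimen start suits the objective.** SAP 3.1.2 concerns ASP2215 combined with induction and consolidation, so one could keep the chemotherapy origin and use delayed entry. That would not recover survival from chemotherapy start, because almost nobody in the set is at risk before ASP2215 begins.
- **An analysis of all starters could mix populations.** SAP 3.2 limits Phase 2 to FLT3-mutated AML, and the SAP does not say why subjects fail registration. This stands, and it restricts the supplementary analysis proposed below.

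A reader might also infer that a full week without deaths is a stated feature of the design, that the two distortions accumulate, or that the trial's main result is compromised. The documents support none of these: there is no stated Phase 2 ASP2215 start day, the two sizes belong to alternative readings, and the primary endpoint is a response rate with no time origin of this kind.

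**Conclusion.** The mismatch is real on the text. A set that requires ASP2215 is combined with an origin that most naturally means chemotherapy, and no planned analysis corrects for it. The direction is upward for both OS and EFS.

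The size is probably modest: about 0.3 to 0.7 points on 12-month OS, given a 7-day gap, a constant hazard and a median OS of 12 to 48 months, all of which are assumptions. An effect of several points would need an early-death share near 5%, for which the SAP offers no evidence. The point is worth correcting because outside comparison is the only use these endpoints have, not because it threatens the trial's conclusion.

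**What to change.** In SAP 6.1.3:

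1. Define *first treatment* explicitly.
2. For Phase 2, time OS and EFS in the TTE-FAS from the date of the first ASP2215 dose, so that the origin matches the entry condition. Move the EFS rule that censors subjects without a post-treatment assessment at treatment start to the same date.
3. If survival from chemotherapy start is also wanted, add it as a supplementary analysis in pre-registered subjects with confirmed FLT3 mutation who started induction chemotherapy, as far as their vital status was collected. If that cannot be done, label any chemotherapy-origin curve as conditional on surviving to, and receiving, ASP2215.

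The cost is a few lines of wording and one changed origin date in the derivation. Sample size, power and trial conduct do not change. Reported medians become about a week shorter if ASP2215 starts on Day 8. The supplementary analysis may be incomplete if follow-up of registration failures was limited.
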